5.1.5 Management of Specific Adverse Events

Study treatment may be delayed for toxicity for a maximum amount of time, as specified in the tables below. If study treatment is delayed for longer than the specified maximum, study treatment will be permanently discontinued. Treatment delays apply to all toxicities described below; dose modifications apply only to toxicities that are considered

to be related to lenalidomide. There will be no dose reductions of obinutuzumab or atezolizumab.

The lenalidomide dose may be reduced in 5-mg increments one or two times, depending on the starting dose, as outlined in [Table 9](#). There will be no more than one dose reduction per treatment cycle. If the lenalidomide dose is reduced, re-escalation is not permitted.

Table 9 Lenalidomide Dose Reduction

Starting Dose	First Reduction	Second Reduction
20 mg	15 mg	10 mg
15 mg	10 mg	5 mg
10 mg	5 mg	—

If a lenalidomide-related toxicity occurs during lenalidomide treatment (i.e., before Day 21 of the cycle), lenalidomide must be withheld until criteria for recovery have been met (i.e., improves to Grade ≤ 2 or baseline values).

If recovery is observed prior or on Day 15 of the cycle, lenalidomide may be resumed at the same dose for the remainder of the cycle (through Day 21; missed doses will not be made up) at the discretion of the investigator. If the investigator considers that resuming lenalidomide at the same dose within the cycle represents an unacceptable risk for the patient, lenalidomide shall be resumed at reduced dose or withheld for the remainder of the cycle. For subsequent cycles, lenalidomide will be resumed at reduced doses.

If recovery is observed after Day 15 of the cycle, lenalidomide will not be resumed for the current cycle. For subsequent cycles, lenalidomide will be resumed at reduced doses.

Guidelines for management of toxicities during induction are provided in [Section 5.1.5.1](#). Guidelines for management of toxicities during maintenance are provided in [Section 5.1.5.2](#).

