3.1.3 Expansion Phase

The expansion phase is designed to further assess the safety and efficacy of the combination of atezolizumab with obinutuzumab plus lenalidomide when given as induction and maintenance treatment.

Approximately 40 patients with FL will be enrolled during the expansion phase and treated as described below. Patients who received lenalidomide at the RP2D during the dose-escalation phase will be pooled with patients treated in the expansion phase. All patients will receive induction treatment as outlined in [Table 2](#).

Table 2 Induction Treatment for Expansion Phase

Cycle(s)	Atezo + G + Len (28-Day Cycles)
1	
 • Lenalidomide at RP2D PO once daily on Days 1–21 • Obinutuzumab 1000 mg IV on Days 1, 8, and 15
2–6	
 • Lenalidomide at RP2D PO once daily on Days 1–21 • Obinutuzumab 1000 mg IV on Day 1 • Atezolizumab 840 mg IV on Days 1 and 15

IV=intravenous; PO=by mouth; RP2D=recommended Phase II dose.

Patients who achieve a CR, a PR, or stable disease at EOI will receive maintenance treatment with Atezo + G + Len, as outlined in [Table 3](#). Maintenance treatment should start 8 weeks (\pm 1 week) after Day 1 of Cycle 6 and will continue until disease progression or unacceptable toxicity for up to 24 months.

Table 3 Maintenance Treatment

Patients with FL	
Maintenance treatment consisting of the following, administered for 24 months (from Months 1–24 ^a):
 
 • Lenalidomide 10 mg PO once daily on Days 1–21 of each month for a maximum of 12 months • Obinutuzumab 1000 mg IV on Day 1 of every other month (i.e., every 2 months), starting with Month 1 • Atezolizumab 840 mg IV on Days 1 and 2 of each month
------------------	---

[figure not shown]
FL=follicular lymphoma; IV=intravenous; PO=by mouth.

^a 1 month=28 days.

In the event that any one of the stopping rules criteria (refer to [Section 6.11](#) for further details) occurs at any time in the expansion phase, enrollment of patients will be paused while an IMC is immediately convened to review and provide a recommendation on further conduct of the study (e.g., consider study discontinuation).

A schedule of assessments is provided in [Appendix 1](#), and a study schema is provided in [Figure 1](#).

Figure 1 Study Schema

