3.3.2.2 Rationale for Obinutuzumab and Lenalidomide Dose and Schedule

Obinutuzumab in combination with lenalidomide is currently being evaluated in an ongoing Phase Ib/II study (MO28005 [GALEN]) in patients with relapsed or refractory FL and aggressive lymphoma (DLBCL and mantle cell). A total of 20 patients with relapsed or refractory FL have been enrolled in the dose-escalation phase of the study and have received escalating doses of oral lenalidomide ranging from 10 to 25 mg/day on Days 1–21 of a 28-day cycle in combination with obinutuzumab at a fixed dose of 1000 mg on Days 8, 15, and 22 of Cycle 1 and on Day 1 of Cycles 2–6. The RP2D of lenalidomide was established as 20 mg/day on the basis of an increased incidence of Grade 3 or 4 neutropenia between Cycles 2 and 6 at the next higher dose of 25 mg/day (Morschhauser et al. 2014). The enrollment in the expansion phase at 20 mg/day is in progress. As of 30 September 2014, 45 patients were evaluable for safety during induction treatment (Cycles 1–6). Preliminary data demonstrate a manageable safety profile (see Section 1.4.3.2). In this study, the starting dose for lenalidomide during induction treatment is 15 mg/day on Days 1–21 of a 28-day cycle, which is one dose level below the RP2D of 20 mg/dose defined in Study MO28005 (GALEN).

During maintenance treatment, the lenalidomide dose will be 10 mg/day on Days 1–21, every month for 12 months. The use of lenalidomide at this dosing regimen in the maintenance setting in lymphoma is currently being evaluated in ongoing Phase Ib/II and Phase III studies in patients with FL, both as a single agent (e.g., RELEVANCE ClinicalTrial.gov, number NCT01476787) and in combination with obinutuzumab (Study MO28005 [GALEN]). The proposed dosing regimen for lenalidomide as maintenance treatment is also supported by the available clinical data from randomized studies in multiple myeloma that evaluate lenalidomide maintenance in patients following stem-cell transplantation (Attal et al. 2013; McCarthy et al. 2012) and in patients ineligible for transplantation (Palumbo et al. 2012). Results from these studies demonstrate a favorable benefit-risk profile of lenalidomide 10-mg maintenance therapy, allowing for continuous long-term treatment in this setting.

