4.2 METHOD OF TREATMENT ASSIGNMENT

This is a Phase Ib/II, open-label, multicenter, non-randomized, dose-escalation study of Atezo+G+Len in patients with relapsed or refractory FL. During the dose-escalation phase, an interactive voice or web-based response system (IxRS) will be used to assign patients to dosing groups that vary according to the dose of lenalidomide given during induction treatment. During the expansion phase, patients will receive lenalidomide at the RP2D during induction treatment. All patients will receive lenalidomide at a dose of 10 mg during maintenance treatment. Atezolizumab and obinutuzumab will be given at stable doses to all patients, during both induction and maintenance treatment.

Enrollment tracking will be performed through use of the IxRS. Prior to initiating screening, the study site should confirm via the IxRS that slots are available for enrollment. After written informed consent has been obtained and preliminary eligibility has been established, the study site will submit documentation supporting eligibility to the Sponsor and obtain the Sponsor's approval to enroll the patient. Once the Sponsor reviews and approves the patient for enrollment, the patient number will be assigned and the patient will be enrolled via the IxRS. The Sponsor will communicate to the sites impending closure of screening.

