4.3.2.3 Lenalidomide

Lenalidomide will be administered orally once daily on Days 1–21 of Cycles 1–6 (28-day cycles) during induction treatment and on Days 1–21 of each month during maintenance treatment. During the dose-escalation phase, lenalidomide will be administered at a dose of 15 or 20 mg (dose may be de-escalated to 10 mg) during induction treatment and at 10 mg during maintenance treatment. During the expansion phase, lenalidomide will be administered at the RP2D during induction treatment and at 10 mg during maintenance treatment.

Lenalidomide capsules should be swallowed whole with water and should not be broken, chewed, or opened. The capsules may be taken with or without food, except on lenalidomide PK sampling days (see [Appendix 2](#)), when the patient should fast (water allowed) at least 2 hours before and at least 1 hour after the lenalidomide dose. On lenalidomide PK sampling visits, lenalidomide dose will be taken in the clinic.

Lenalidomide should be administered at approximately the same time each day. If a dose of lenalidomide is missed and it has been < 12 hours since the time of the scheduled dose, the patient may take the missed dose. If it has been > 12 hours, the dose should be skipped and the next dose should be taken at the regularly scheduled time. Two doses should not be taken at the same time. If a dose had been vomited, the dose should not be re-taken.

At each cycle, each patient will be supplied with only enough lenalidomide for that cycle. A drug diary will be provided to the patient to record oral administration of doses, including the date and time. Patients will be instructed to return empty bottles or unused capsules. The investigator is responsible for monitoring patient compliance by monitoring the patient diary and counting unused capsules.

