4.3.2.5 Maintenance Treatment with Atezolizumab, Obinutuzumab, and Lenalidomide (Atezo+G+Len)

Patients who achieve a CR, a PR, or stable disease at EOI are eligible for maintenance treatment with atezolizumab and obinutuzumab for 24 months and lenalidomide for 12 months, as outlined in [Table 5](#).

Lenalidomide will be given before other agents are administered on the same day. Obinutuzumab will be administered next, followed by a line flush (unless there is a central line with more than one line/port), after which atezolizumab will be administered.

Maintenance treatment should start 8 weeks (\pm 1 week) after Day 1 of Cycle 6 and will continue until disease progression or unacceptable toxicity for up to 24 months.

Table 5 Maintenance Treatment

Treatment	Dose	Route	Regimen (Months 1–24)
Lenalidomide	10 mg	PO	Days 1–21 of each month for a maximum of 12 months
Obinutuzumab	1000 mg	IV	Day 1 of every other month (i.e., every 2 months), starting with Month 1
Atezolizumab	840 mg	IV	Days 1 and 2 of each month

IV=intravenous; PO=by mouth.

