Grade 3 or 4 hematologic toxicity ^{a,b}	
For patients on any dose of lenalidomide:
 
 • If toxicity occurs before Cycle 1 Day 8 or Cycle 1 Day 15, these doses of obinutuzumab will not be skipped but given after resolution of toxicity. 
For patients on a lenalidomide dose ≥ 10 mg who have had one or no prior lenalidomide dose reductions
 
 • Withhold study treatment (except atezolizumab).^c • Administer RBCs or platelets as required. • If patient has not already initiated G-CSF, initiate prophylactic G-CSF for current and subsequent cycles. • For patients receiving primary thromboprophylaxis who develop platelet count of $< 20,000/\mu\text{L}$, reduce the dose of LMWH or consider temporarily withholding platelet inhibitors, as applicable. If patient's condition doesn't allow interruption of the anticoagulant/anti-aggregant treatment, adequate platelet transfusion support and close monitoring of the hematologic and coagulation functions are required. • For lenalidomide dose reductions, refer to guidelines presented in Section 5.1.5. • If the event is ongoing on Day 1 of the next cycle but improves to Grade ≤ 2 or baseline ≤ 14 days after the scheduled date of the cycle, resume obinutuzumab at full dose and resume lenalidomide at current dose or reduced dose if the patient received < 21 days of lenalidomide due to toxicity (see Section 5.1.5). • If the event is ongoing on Day 1 of the next cycle but improves to Grade ≤ 2 or baseline 15–21 days after the scheduled date for the next cycle, resume obinutuzumab at full dose and resume lenalidomide at a reduced dose^{a, b} per guidelines in Section 5.1.5^{a, b} for current and subsequent cycles. • If study treatment is withheld for > 21 days, permanently discontinue lenalidomide. Obinutuzumab may be continued for patients experiencing clinical benefit as determined by the investigator after discussion with the Medical Monitor. • Permanently discontinue study treatment if any of the following events occur: 
 Grade 3 or 4 thrombocytopenia that results in significant bleeding per investigator judgment Recurrent Grade 3 or 4 neutropenia associated with fever $> 38^\circ\text{C}$ lasting > 5 days or documented infection despite use of G-CSF and after one lenalidomide dose reduction Recurrent Grade 4 neutropenia or thrombocytopenia lasting > 7 days despite use of G-CSF (for neutropenia) and after one lenalidomide dose reduction 
For patients on a lenalidomide dose of 5 mg and patients who have had two prior lenalidomide dose reductions:
 
 • Permanently discontinue lenalidomide. Obinutuzumab may be continued for patients experiencing clinical benefit as determined by the investigator after discussion with the Medical Monitor.

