5.1.5.2 Toxicities during Maintenance Treatment

Table 12 provides guidelines for management of toxicities that occur during maintenance treatment.

Table 12 Guidelines for Management of Toxicities That Occur during Maintenance Treatment

Event	Action To Be Taken
Hematologic toxicity: Grade 3 or 4	For all patients: 
• Atezolizumab may be continued at the discretion of the investigator.• Withhold obinutuzumab and lenalidomide.• Administer G-CSF for neutropenia per institutional guidelines.• Administer RBCs or platelets as required.• If there is improvement to Grade ≤ 2, resume obinutuzumab and lenalidomide at same dose.• If study treatment is withheld for > 42 days, permanently discontinue study treatment.
Non-hematologic toxicity: Grade ≥ 2	For atezolizumab-related toxicities with possible immune etiology: 
• Follow guidelines presented in Table 11 for the management of atezolizumab-related toxicities with possible immune etiology (i.e., autoimmune colitis, hepatitis, pancreatitis, hypothyroidism, pneumopathy, skin, toxicity, or ocular toxicity). For all other non-hematologic toxicities: 
• Withhold study treatment.• If there is improvement to Grade ≤ 1 or baseline, administer study treatment at full dose.• If study treatment is withheld for > 42 days, permanently discontinue study treatment.

G-CSF = granulocyte colony-stimulating factor.

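### The ban on lenalidomide re-escalation and the fixed 10 mg maintenance dose conflict for a patient who ends induction on 5 mg

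*Combined protocol and SAP*

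**What the plan says.** **Reductions.** Section 5.1.5 allows lenalidomide to be lowered in 5 mg steps, at most once per cycle, for toxicity attributed to lenalidomide. Table 9 gives the ladder by starting dose. The section then says: "If the lenalidomide dose is reduced, re-escalation is not permitted". No phase is named, and the same section introduces both the induction guidance (5.1.5.1) and the maintenance guidance (5.1.5.2). Table 10 treats 5 mg as a working induction dose, with a row "For patients on a lenalidomide dose of 5 mg and patients who have had two prior lenalidomide dose reductions". In that row, Grade 3 or 4 hematologic toxicity ends lenalidomide for good.

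**Maintenance dose.** Section 4.2 says "All patients will receive lenalidomide at a dose of 10 mg during maintenance treatment". Section 4.3.2.3 and the synopsis say, for the expansion phase, that "lenalidomide will be administered at the RP2D during induction treatment and at 10 mg during maintenance treatment". Section 3.3.2.2 says "During maintenance treatment, the lenalidomide dose will be 10 mg/day on Days 1–21, every month for 12 months". Table 3 has "Lenalidomide 10 mg PO once daily on Days 1–21 of each month for a maximum of 12 months", and Table 5 repeats the 10 mg dose on the same schedule. None of these places mentions a patient already reduced below 10 mg.

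**Toxicity in maintenance.** For Grade 3 or 4 hematologic toxicity, Table 12 tells the site, after recovery to Grade 2 or better, to "resume obinutuzumab and lenalidomide at same dose". For non-hematologic toxicity without a suspected immune cause it calls for the full dose after recovery. It contains no reduction step.

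**Renal dosing.** The renal row of Table 11 gives 10 mg every other day when creatinine clearance is below 30 mL/min without dialysis, and 5 mg/day with dialysis, whatever the starting dose. Section 5.1.5.1 presents Table 11 as induction guidance. Table 12 refers back to it only for atezolizumab-related events of possible immune origin.

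**The concern.** A patient taken down to 5 mg has, by the protocol's own definition, shown toxicity attributed to lenalidomide. If that patient has a complete response, partial response or stable disease at the end of induction, the maintenance dosing text gives 10 mg and Section 5.1.5 appears to forbid it. Two sites could treat the same patient differently, and each could cite the protocol.

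The safety logic also reverses at the phase boundary. In induction, a Grade 3 or 4 hematologic event on 5 mg ends lenalidomide. In maintenance, the same event on 10 mg leads, after recovery, to resumption at an unchanged dose. Blood counts become less frequent at the same time. Appendix 1 schedules hematology on Days 1 and 15 of Cycles 2–6 (with Days 8 and 22 added in Cycles 2 and 3), but monthly in maintenance.

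**Working it through.** **1. Lowest induction dose under Table 9.** Floor = starting dose − 5 mg × number of reductions allowed.

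- 20 mg start: 20 − 2 × 5 = 10 mg
- 15 mg start: 15 − 2 × 5 = 5 mg
- 10 mg start: 10 − 1 × 5 = 5 mg

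These reproduce Table 9.

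**2. Change of dose on entering maintenance.** Ratio = 10 mg ÷ last induction dose.

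| Starting dose | Doses reachable in induction | Ratio at each |
|---|---|---|
| 20 mg | 20, 15, 10 | 0.50, 0.67, 1.00 |
| 15 mg | 15, 10, 5 | 0.67, 1.00, 2.00 |
| 10 mg | 10, 5 | 1.00, 2.00 |

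On this ladder only a patient who ends on 5 mg has an increase, and it is a doubling.

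**3. Amount of drug (Table 5 schedule).** Per 28-day month: 21 × 5 = 105 mg against 21 × 10 = 210 mg. Over the maximum of 12 months, 21 × 12 = 252 dosing days: 252 × 5 = 1260 mg against 252 × 10 = 2520 mg, if nothing is withheld.

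**4. How many patients start at a dose from which 5 mg can be reached.** Escalation groups are 3–6 patients each (Section 3.1.2) and expansion is about 40 (Section 3.1.3).

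- RP2D 20 mg: the 15 mg group only, 3–6.
- RP2D 15 mg: 3 + 40 to 6 + 40 = 43–46.
- RP2D 10 mg: 3 + 3 + 40 to 6 + 6 + 40 = 46–52.

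These count everyone who starts at such a dose, so they are loose ceilings and not estimates of those affected. They also leave out replacement patients (Sections 3.1.2 and 4.6.2). The documents give no rate of reduction to 5 mg. The obinutuzumab–lenalidomide study described in Section 1.4.3.2 had a median induction dose intensity above 98% for both drugs. That suggests reductions may be uncommon, although a median does not exclude a reduced minority.

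**5. Renal route.** 10 mg every other day averages 10 ÷ 2 = 5 mg/day, and the dialysis dose is 5 mg/day. A patient who started at 20 mg can therefore also be below 10 mg/day.

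**6. Which rule governs.** If the ban in Section 5.1.5 runs through the whole study, it forbids 5 to 10 mg and contradicts the maintenance dosing text. If it covers induction only, which its wording in terms of starting doses and cycles allows, the formal contradiction disappears but the doubling stands. Nothing in the documents settles this.

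**The case against.** The strongest reply is that a specific rule about reduced patients should prevail over general dosing lines. The ban is in the parent section of both sets of guidance and has no phase limit, so a careful site would keep the patient at 5 mg. Table 12's instruction to resume at the same dose fits a carried-over 5 mg. This part stands, and it rules out a stronger reading. A reader might infer that the protocol has no rule carrying a reduction into maintenance, and so requires the doubling. Section 5.1.5 does contain a rule that can be read that way. What is missing is a statement that it prevails over text addressed to all patients.

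The path is also narrow. A 15 mg starter needs two lenalidomide-related reductions within six cycles. That patient must also avoid the Table 10 discontinuation rules, have no further Grade 3 or 4 hematologic event on 5 mg, and have at least stable disease at the end of induction. This stands too, and is why the number is probably small.

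Finally, there are safeguards:

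- Section 4.6.2 stops treatment for life-threatening events, and for related non-immune events that stay at Grade 3 or above, or force withholding, beyond 21 days.
- Section 4.6.2 also allows one drug to be dropped while the other two continue.
- Table 12 stops treatment after more than 42 days of withholding.
- Maintenance starts 8 weeks (±1) after Day 1 of Cycle 6, so 56 − 21 = 35 days pass without lenalidomide first.

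The stopping rules limit harm after toxicity appears, and the gap gives time to recover. None of them sets the dose at which maintenance begins.

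**Conclusion.** The point holds as an unresolved conflict between two stated rules. Following the maintenance dosing text would give a patient reduced to 5 mg for lenalidomide-related toxicity twice the last induction dose, with no step down in Table 12. This assumes only that such a patient enters maintenance still on 5 mg and that the site follows the 10 mg text.

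How many patients this concerns cannot be derived from the documents. With an RP2D of 20 mg, Table 9 exposes nobody in the expansion phase and about 3–6 escalation patients plus replacements. With 15 or 10 mg, expansion patients could be exposed as well. A reader might infer from Table 9 that no 20 mg starter can be concerned. The renal row of Table 11 shows otherwise, because it can take any patient below 10 mg/day and is not expressly extended to maintenance.

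Nor should a reader infer a threat to the main efficacy result. Complete response at the end of induction is determined before maintenance, since the end-of-induction response decides who enters it. This is a dosing and safety point that should be corrected. It changes no sample size, precision or primary analysis figure.

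**What to change.** 1. In Section 4.3.2.5 and Table 5, state the maintenance lenalidomide dose as 10 mg or the patient's last toxicity-reduced induction dose, whichever is lower. Put matching text in the synopsis, Table 3 and Sections 3.3.2.2, 4.2 and 4.3.2.3.
2. In Section 5.1.5, state that the ban on re-escalation continues into maintenance.
3. In Table 12, define the same dose and the full dose, for lenalidomide, as the patient's current maintenance dose.
4. State that the creatinine-clearance adjustments in Table 11 also apply in maintenance.

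The cost is protocol wording in a handful of places. Section 4.3.1.3 already provides 5 mg capsules. Visits, sample size and the primary analysis do not change.

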5.1.5.1 Toxicities during Induction Treatment

Hematologic Toxicities during Induction Treatment

[Table 10](#) provides guidelines for management of hematologic toxicities that occur during induction treatment. Hematologic toxicity is defined as neutropenia, anemia, or thrombocytopenia. Lymphopenia is not considered a hematologic toxicity but rather an expected outcome of therapy.

Table 10 Guidelines for Management of Hematologic Toxicities that Occur during Induction Treatment

Event	Action To Be Taken
Grade 3 or 4 hematologic toxicity ^{a,b}	
For patients on any dose of lenalidomide:
 
 • If toxicity occurs before Cycle 1 Day 8 or Cycle 1 Day 15, these doses of obinutuzumab will not be skipped but given after resolution of toxicity. 
For patients on a lenalidomide dose ≥ 10 mg who have had one or no prior lenalidomide dose reductions
 
 • Withhold study treatment (except atezolizumab).^c • Administer RBCs or platelets as required. • If patient has not already initiated G-CSF, initiate prophylactic G-CSF for current and subsequent cycles. • For patients receiving primary thromboprophylaxis who develop platelet count of $< 20,000/\mu\text{L}$, reduce the dose of LMWH or consider temporarily withholding platelet inhibitors, as applicable. If patient's condition doesn't allow interruption of the anticoagulant/anti-aggregant treatment, adequate platelet transfusion support and close monitoring of the hematologic and coagulation functions are required. • For lenalidomide dose reductions, refer to guidelines presented in Section 5.1.5. • If the event is ongoing on Day 1 of the next cycle but improves to Grade ≤ 2 or baseline ≤ 14 days after the scheduled date of the cycle, resume obinutuzumab at full dose and resume lenalidomide at current dose or reduced dose if the patient received < 21 days of lenalidomide due to toxicity (see Section 5.1.5). • If the event is ongoing on Day 1 of the next cycle but improves to Grade ≤ 2 or baseline 15–21 days after the scheduled date for the next cycle, resume obinutuzumab at full dose and resume lenalidomide at a reduced dose^{a, b} per guidelines in Section 5.1.5^{a, b} for current and subsequent cycles. • If study treatment is withheld for > 21 days, permanently discontinue lenalidomide. Obinutuzumab may be continued for patients experiencing clinical benefit as determined by the investigator after discussion with the Medical Monitor. • Permanently discontinue study treatment if any of the following events occur: 
 Grade 3 or 4 thrombocytopenia that results in significant bleeding per investigator judgment Recurrent Grade 3 or 4 neutropenia associated with fever $> 38^\circ\text{C}$ lasting > 5 days or documented infection despite use of G-CSF and after one lenalidomide dose reduction Recurrent Grade 4 neutropenia or thrombocytopenia lasting > 7 days despite use of G-CSF (for neutropenia) and after one lenalidomide dose reduction 
For patients on a lenalidomide dose of 5 mg and patients who have had two prior lenalidomide dose reductions:
 
 • Permanently discontinue lenalidomide. Obinutuzumab may be continued for patients experiencing clinical benefit as determined by the investigator after discussion with the Medical Monitor.

G-CSF = granulocyte colony-stimulating factor; LMWH = low-molecular-weight heparin.

^a Dose modifications apply only to events that are considered to be related to lenalidomide.

^b If cytopenia is thought to be caused mainly by non-Hodgkin's lymphoma infiltration of the bone marrow, the investigator may decide not to reduce the dose of lenalidomide.

^c For Grade 3 neutropenia, only if sustained (≥ 7 days) Grade 3 or \geq Grade 3 associated with fever (temperature $\geq 38.5^\circ\text{C}$).

Non-Hematologic Toxicities during Induction Treatment

[Table 11](#) provides guidelines for management of non-hematologic toxicities that occur during induction treatment.

Toxicities associated or possibly associated with atezolizumab treatment should be managed according to standard medical practice. Additional tests, such as autoimmune serology or biopsies, should be used to evaluate for a possible immunogenic etiology. For detailed information regarding management of adverse events associated with atezolizumab, please refer to the [Appendix 10](#).

Table 11 Guidelines for Management of Non-Hematologic Toxicities

Event	Action to Be Taken
General guidance for treatment delays and discontinuation	
 • If toxicity occurs before Cycle 1 Day 8 or Cycle 1 Day 15, these doses of obinutuzumab will not be skipped but given after resolution of toxicity. • When a treatment cycle is delayed because of a toxicity resulting from any component of the regimen, all study treatment should generally be held and resumed together to remain synchronized. • If it is anticipated that atezolizumab will be delayed by >21 days, obinutuzumab and lenalidomide should be given without atezolizumab if there is no contraindication. • If one drug is discontinued, treatment with the other two drugs may be continued for patients experiencing clinical benefit as determined by the investigator after discussion with the Medical Monitor. • Permanently discontinue study treatment if any of the following events occur: 
 – Grade ≥ 3 non-immune-mediated adverse event that is considered to be related to study treatment and does not resolve to Grade ≤ 2 within 21 days – Non-immune-mediated adverse event that is considered to be treatment related and requires study treatment to be withheld for >21 days – Immune-mediated adverse event that requires atezolizumab to be withheld for >42 days, unless approved by the Medical Monitor
IRRs and anaphylaxis	
 • Guidelines for management of IRRs are provided in Sections 4.3.2.1 (obinutuzumab) and 4.3.2.2 (atezolizumab). • Metamizole (dipyrone) is prohibited in treating atezolizumab-associated IRRs because of its potential for causing agranulocytosis. • In case of anaphylaxis, study treatment should be permanently discontinued.
Renal toxicity	
 • Adjust the dose of lenalidomide^a as outlined below: 
 – If creatinine clearance is ≥ 30 but < 60 mL/min, lenalidomide should be given at a dose of 10 mg/day. – If creatinine clearance is < 30 mL/min and dialysis is not required, lenalidomide should be given at a dose of 10 mg every other day. – If creatinine clearance is < 30 mL/min and dialysis is required, lenalidomide should be given at a dose of 5 mg/day. On dialysis days, the dose should be administered after dialysis.

Table 11 Guidelines for Management of Non-Hematologic Toxicities (cont.)

	Event	Action to Be Taken
TLS	Clinical TLS ^b	
 • Withhold study treatment. • Correct electrolyte abnormalities, monitor renal function and fluid balance, and administer supportive care, including dialysis as indicated. Rasburicase therapy (if approved by the local health authority) may be administered as needed to reduce hyperuricemia. • If symptoms resolve completely, resume atezolizumab and obinutuzumab at full dose and resume lenalidomide at a reduced dose^a per guidelines in Section 5.1.5 for current and subsequent cycles. • Perform chemistry panel every other day for the first week after re-initiation of lenalidomide.
	Laboratory TLS ^b	
 • Withhold study treatment. • Correct electrolyte abnormalities, monitor renal function and fluid balance, and administer supportive care as clinically indicated. • If laboratory abnormalities have resolved completely, resume atezolizumab and obinutuzumab at full dose and resume lenalidomide either at current dose or at a reduced dose^a per guidelines in Section 5.1.5 for current and subsequent cycle, at the investigator's discretion.
Peripheral neuropathy	Grade 4 or Myasthenia gravis (any grade) or Guillain-Barre (any grade)	
 • Permanently discontinue study treatment. • Initiate treatment as per institutional guidelines.
	Grade 2 or 3	
 • Withhold study treatment and evaluate patient at least every 7 days. • If neurotoxicity is considered likely related to lenalidomide and there is improvement to Grade \leq 1 or baseline, resume atezolizumab and obinutuzumab at full dose and resume lenalidomide at a reduced dose^a per guidelines in Section 5.1.5 for current and subsequent cycles. • Permanently discontinue atezolizumab for life-threatening immune-mediated neuropathy.
New-onset neurologic manifestations suggestive of progressive multifocal leukoencephalopathy		
 • Withhold study treatment.^a • Consult with a neurologist if progressive multifocal leukoencephalopathy is suspected (refer to Section 5.1.1.5 for guidance on investigations). • If progressive multifocal leukoencephalopathy is ruled out, resume atezolizumab and obinutuzumab at full dose and resume lenalidomide at current dose. • If progressive multifocal leukoencephalopathy is confirmed, permanently discontinue study treatment.

Table 11 Guidelines for Management of Non-Hematologic Toxicities (cont.)

Event	Action to Be Taken	
Immune-mediated meningoencephalitis	
 • Withhold study treatment. • Refer patient to neurologist. • Initiate treatment with 1–2 mg/kg/day IV methylprednisolone or equivalent and convert to 1–2 mg/kg/day oral prednisone or equivalent upon improvement. If event does not improve within 48 hours after initiating corticosteroids, consider adding an immunosuppressive agent. • If event resolves to Grade 1: 
 – Resume obinutuzumab at full dose and lenalidomide at current dose. – Taper corticosteroids over 1 month. Contact Medical Monitor before resuming atezolizumab. 	
Immune-mediated nephritis	Grade 3 or 4	
 • Permanently discontinue study treatment. • Refer patient to renal specialist. • Consider renal biopsy and supportive measures. • Corticosteroids and/or additional immunosuppressive agents should be administered as clinically indicated. • If event resolves to Grade 1 or better, taper corticosteroids over ≥ 1 month.
	Grade 2	
 • Withhold atezolizumab for up to 12 weeks after event onset.^d Contact Medical Monitor. • Refer patient to renal specialist. • Consider renal biopsy and supportive measures as indicated. • Corticosteroids and/or additional immunosuppressive agents should be administered as clinically indicated. • If event resolves to Grade 1 or better, resume atezolizumab.^e • If event does not resolve to Grade 1 or better while withholding atezolizumab, permanently discontinue atezolizumab and contact Medical Monitor.^f
	Grade 1	
 • Continue study treatment. • Monitor kidney function, including creatinine, closely until values resolve to within normal limits or to baseline values.

Table 11 Guidelines for Management of Non-Hematologic Toxicities (cont.)

AST, ALT, or bilirubin increase	Grade ≥ 3 (or $\geq 10 \times$ ULN for patients with liver involvement)	
 • Withhold study treatment and monitor liver enzymes at least every 7 days. • Investigate etiology. Consult with a hepatologist if immune etiology is suspected (refer to Appendix 10 for guidance in case of suspected immune-mediated hepatitis). • For immune-mediated hepatopathy: 
 - Treat with corticosteroids following guidance provided in the Appendix 10. - Permanently discontinue atezolizumab - Obinutuzumab may be resumed at full dose and lenalidomide at reduced dose for current and subsequent cycles as specified below, at investigator's discretion and after approval by the Medical Monitor. • If immune etiology is unlikely and there is improvement to Grade ≤ 1, resume obinutuzumab and atezolizumab at full dose and resume lenalidomide at a reduced dose^a per guidelines in Section 5.1.5 for current and subsequent cycles.
	Grade 2 lasting > 5–7 days	
 • Withhold atezolizumab. • If immune etiology is suspected, treat with corticosteroids according to guidance provided in the Appendix 10. • If there is improvement to Grade ≤ 1, resume atezolizumab after corticosteroids have been tapered (refer to Appendix 10 for guidance). Contact Medical Monitor before resuming atezolizumab.
Amylase or lipase increase +/- abdominal pain	Grade ≥ 3	
 • Withhold study treatment. • Investigate etiology. Consult with a gastroenterologist if immune etiology is suspected. • For isolated increase of lipase or amylase that is asymptomatic and considered related to atezolizumab, obinutuzumab/rituximab and lenalidomide may be continued at current dose at the investigator's discretion and in discussion with the Medical Monitor. • If no improvement, consider treatment with corticosteroids equivalent to 1–2 mg/kg/day oral prednisone. • If there is improvement to Grade ≤ 2 and patient is asymptomatic, resume obinutuzumab at full dose and resume lenalidomide at current dose. Atezolizumab may be resumed at full dose after approval by the Medical Monitor. • For recurrent Grade 3 lipase or amylase increase that is isolated and asymptomatic, atezolizumab may be resumed following an individual benefit/risk assessment and in discussion with the Medical Monitor.

Table 11 Guidelines for Management of Non-Hematologic Toxicities (cont.)

Event		Action to Be Taken
Amylase or lipase increase +/- abdominal pain (cont.)	Grade 2 long lasting (e.g., > 3 weeks)	
Amylase and/or lipase >1.5–2.0 ×ULN:
 
 Continue study treatment. Consider oral prednisone 10 mg daily or equivalent. 
Asymptomatic with amylase and/or lipase > 2.0–5.0 × ULN:
 
 Treat as a Grade 3 event.
Immune-mediated pancreatitis	Grade 4	
 Permanently discontinue atezolizumab and contact Medical Monitor. ^f Refer patient to gastrointestinal specialist. Initiate treatment with corticosteroids equivalent to 1–2 mg/kg/day IV methylprednisolone and convert to 1–2 mg/kg/day oral prednisone or equivalent upon improvement. If event does not improve within 48 hours after initiating corticosteroids, consider adding an immunosuppressive agent. If event resolves to Grade ≤ 1, taper corticosteroids over ≥ 1 month.
	Grade 2 or 3	
 Withhold atezolizumab for up to 12 weeks after event onset. ^d Refer patient to gastrointestinal specialist. Initiate treatment with corticosteroids equivalent to 1–2 mg/kg/day IV methylprednisolone and convert to 1–2 mg/kg/day oral prednisone or equivalent upon improvement. If event resolves to Grade 1 or better, resume atezolizumab. ^e If event does not resolve to Grade 1 or better while withholding atezolizumab, permanently discontinue atezolizumab and contact Medical Monitor. ^f For recurrent events, permanently discontinue atezolizumab and contact Medical Monitor. ^f
Ocular toxicity	Grade 3 or 4	
 Withhold study treatment. Investigate etiology. Consult with an ophthalmologist. Treat immune-mediated toxicity attributable to atezolizumab with systemic corticosteroids equivalent to 1–2 mg/kg/day oral prednisone. If there is improvement to Grade ≤ 1, resume obinutuzumab at full dose and resume lenalidomide at current dose. Taper corticosteroids over ≥ 1 month. Permanently discontinue atezolizumab.

Table 11 Guidelines for Management of Non-Hematologic Toxicities (cont.)

Event		Action to Be Taken
Ocular toxicity (cont.)	Grade 2	
 • Withhold study treatment for up to 12 weeks after event onset. ^d • Consult with an ophthalmologist. • Treat with topical corticosteroid eye drops and topical immunosuppressive therapy. • If event resolves to Grade ≤ 1, resume study treatment. ^e • If event does not resolve to Grade ≤ 1 while withholding atezolizumab, permanently discontinue atezolizumab and contact Medical Monitor. ^f
	Grade 1	
 • Continue study treatment. • Consult with an ophthalmologist. • Treat with topical corticosteroid eye drops. If symptoms persist, topical immunosuppressive therapy may also be considered. • If symptoms persist, treat as a Grade 2 event.
Diarrhea/Colitis	Grade 4	
 • Permanently discontinue study treatment. • Investigate etiology. Consult with a gastroenterologist (refer to Appendix 10 for guidance in case of suspected immune-mediated colitis). • Treat with corticosteroids following guidance provided in the Appendix 10.
